3.2.3.6.2 Randomization (Visit 2)

Within 1 month, eligible patients should return to the clinic for a Randomization visit. The remaining Randomization procedures should be completed. Lumbar spine, and total body and distal forearm scans (in the 10% subset) obtained within 3 months prior to the screening visit that comply with the study DXA procedures (as described in the Synarc DXA manual) may be used, and need not be redone at Randomization.

Please note that patients cannot be randomized until the BMD QA center and central radiologist have reviewed DXA and lateral spine films and confirm eligibility and stratification.

PK Sample

PK is obtained in the Lead Cohort only. It is essential to accurately record the date and time that the PK sample is drawn, and enter this into the patient database. Patients will be given the first bottle of blinded study therapy. Patients are allowed to choose the day of the week on which to take the blinded study therapy, and should record each day that blinded study therapy and study-supplied Vitamin D₃ is taken on their diary cards. For patients who have signed an informed consent but are not randomized, the investigator

Product: MK-0822

19

Protocol/Amendment No.: 018-04

must submit limited information to the SPONSOR as outlined in the Data Handling Guidelines. Source documentation for nonrandomized patients should remain on file at the site, and is subject to the same retention requirements as data for randomized patients.

Table 3-2 lists the procedures to be performed at the Randomization visit.

Table 3-2

List of Procedures – Randomization (Visit 2)

Review inclusion/exclusion criteria Perform BMD at the lumbar spine Perform distal forearm and total body BMD [§] Perform complete physical exam (including vital signs, height and weight) Collect blood and urine for laboratory efficacy assessments and archives [‡] Collect PK sample in first 1500 patients enrolled Perform ECG Dispense study medication (blinded study therapy, vitamin D ₃ , and calcium for patients with daily calcium intake < 1200 mg) Provide diary card Review diary card Review adverse experiences Review concomitant medications Perform Health Resource Utilization (if fracture has occurred) Collect plasma for proteomics archive Obtain informed consent for genetic sampling [†] Collect genetic sample [†]
[†] May be done at Randomization or any subsequent visit. [‡] Efficacy lab tests are performed on a 10% subset of patients. Archives should be collected in all patients. All samples should be fasting specimens, and urine should be second morning void. [§] BMD of the distal forearm and total body performed on a 10% subset of patients. Patients who had BMD at the lumbar spine performed at screening (Visit 1) do not need to perform this procedure at Randomization (Visit 2).

3.2.3.6.3 Months 3, 9, 18, 30 and 42 (Visits 3, 5, 8, 12, and 16)**PK Sample**

PK is obtained in the Lead Cohort only (Months 3 and 9). It is essential to accurately record the date and time that the PK sample is drawn, and enter this into the patient database. In addition, the time (as well as the date) of the two doses of blinded therapy taken prior to the PK draw must be entered.

Meal Questionnaire

It is extremely important to enter into the patient database whether the patient's dose of blinded study therapy prior to the PK draw was taken without food, with a light meal, or with a full meal. As a guideline, "without food" is within 4 hours before, or 30 minutes

Product: MK-0822

20

Protocol/Amendment No.: 018-04

after blinded study therapy, a "light meal" is considered a light breakfast (e.g. a piece of toast) or snacks, and a "full meal" is considered a robust/solid breakfast or lunch or dinner. Because PK is only performed in the Lead Cohort, the Meal Questionnaire is only administered in the Lead Cohort as well.

The procedures performed at these visits are summarized in Table 3-3 below.

Table 3-3

List of Procedures – Months 3, 9, 18, 30, and 42[†] (Visits 3, 5, 8, 12, and 16)

Perform limited physical exam (including vital signs and weight) Collect blood and urine for laboratory safety assessments [‡] Meal Questionnaire in first 1500 patients enrolled [§] Collect PK sample in first 1500 patients enrolled [§] Dispense study medication (blinded study therapy, vitamin D ₃ , and calcium [if needed]) Provide diary card Review diary card Perform tablet count for compliance (only for blinded study therapy) Review adverse experiences Review concomitant medication Perform Health Resource Utilization (if fracture has occurred)
[†] Since this is an event-driven study that will be stopped once a pre-defined number of fracture events have occurred, not all patients may have all visits detailed in the flow-chart. [‡] Laboratory tests for safety assessments need not be drawn in a fasted state. [§] Months 3 and 9 only.

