3.2.3.6.1 Screening (Visit 1)

Prior to coming into the study clinic, potential participants may be pre-screened by imaging (e.g. ultrasound, DXA, x-ray), by phone, chart review, personal interview, physician referral, or available databases, for eligibility criteria that can be assessed in this manner (e.g. age, concomitant therapies, medical conditions, etc.). Those patients who are interested and seem eligible should be invited to the clinic for a formal screening visit. During this visit, study procedures and requirements should be explained and informed consent obtained by the investigator or physician sub-investigator prior to performing any screening procedures. All patients signing a consent form will be given a unique screening number (a "Baseline Number"), generated by the patient database (EDC), that will be used to identify the patient during the screening period for data collection purposes. Each patient will be assigned only one baseline number.

"Candidate for osteoporosis therapy" and Inclusion/Exclusion Criteria

Several entry criteria refer to the prospective study participant's candidacy for osteoporosis therapy (with regard to bisphosphonates, strontium, or PTH). A candidate for osteoporosis therapy is one who has no contraindications to, or is not intolerant of, or would not refuse treatment with bisphosphonates, strontium, or PTH. A patient who is *not* a suitable candidate is one who has contraindications to, or is intolerant of, or would refuse treatment with bisphosphonates, strontium, or PTH (please refer to Operations Manual for further detail).

Product: MK-0822

16

Protocol/Amendment No.: 018-04**BMD**

Study eligibility regarding BMD criteria will be confirmed by the BMD QA center prior to Randomization. However, sites may determine per local review of the scans that patients with both total hip and femoral neck T-scores > -1.5 are ineligible for the study, and should not send these scans to the QA center or proceed further with screening. Note that lumbar spine BMD will not be considered with regard to study eligibility. Whenever possible, BMD should be performed prior to lateral spine x-rays. Hip BMD scans obtained within 90 days prior to the Randomization visit that comply with the study DXA procedures (as described in the Synarc DXA manual) may be used for study entry.

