Note: Spine DXA at screening will *only* be performed in regions where this is required by regulatory agency via documented request, subsequently approved by the SPONSOR.

Lateral Spine Films

Lateral spine films will also be read centrally to determine study eligibility and the stratum to which the patient will be randomized. Lateral spine films obtained within 90 days prior to the Randomization visit that comply with the study x-ray procedures (as described in the Synarc x-ray manual) may be used for study entry.

Safety Laboratory Tests

Lab values that are outside of limits of normal for this population, which the investigator consider to be clinically significant and that are not explained by a clinical diagnosis, should be discussed with the SPONSOR.

Serum Creatinine

Patients with serum creatinine ≤ 1.6 mg/dL need not undergo further evaluation for renal function, and are eligible for the study.

Patients with serum creatinine > 1.6 mg/dL and calculated creatinine clearance ≥ 60 mL/min are eligible for the study, without further evaluation of renal function.

Patients with severe renal insufficiency (National Kidney Foundation K/DOQI Guidelines) defined as serum creatinine > 1.6 mg/dL and calculated creatinine clearance ≤ 29 mL/min are not eligible, and further evaluation of renal function should not be performed.

Note: Patients with calculated creatinine clearance ≤ 29 mL/min using the Cockcroft-Gault formula are ineligible *only* in those regions where this is required via documented regulatory request, subsequently approved by the SPONSOR.

Patients with moderate renal insufficiency, defined as serum creatinine > 1.6 mg/dL and calculated creatinine clearance 30 – 59 mL/min must return to the clinic to undergo a blood draw for serum PTH and serum 25-hydroxyvitamin D. These patients may be

Product: MK-0822

17

Protocol/Amendment No.: 018-04

included provided that serum PTH, serum 25-hydroxyvitamin D, serum calcium (from screening) and serum phosphorus (from screening) are *all* within normal limits. Calculated creatinine clearance will be done using the Cockcroft-Gault method:

$$Cl_{cr} = \left[\frac{(140 - age)(wt[kg])}{72 \cdot C_s} \right] * 0.85 \text{ with } C_s = \text{serum creatinine and result reported in mL/min.}$$

Parathyroid Hormone (PTH) and 25-hydroxyvitamin D

PTH will be measured at screening in patients with a documented history of parathyroid disease.

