- $\tilde{V} = \left[\frac{\tilde{p}_1(1 - \tilde{p}_1)}{n_1} + \frac{\tilde{p}_2(1 - \tilde{p}_2)}{n_2} \right] \frac{(n_1 + n_2)}{(n_1 + n_2 - 1)}$;
- n_1 and n_2 are the sample sizes for Group 1 and Group 2, respectively;
- \tilde{p}_1 = the maximum likelihood estimate of the proportion for Group 1 and is computed as $\tilde{p}_1 = \tilde{p}_2 + \theta$;
- \tilde{p}_2 = the maximum likelihood estimate of the proportion for Group 2 as a function of θ and under the constraint $\tilde{p}_1 - \tilde{p}_2 = \theta$.

However, since the equation does not allow for explicit solutions for θ , a numerical algorithm will be used to obtain the roots for θ . Details of the numerical algorithm can be found in Miettinen and Nurminen [6].

To account for the variable period of observation between the patients, the denominators in the above proportions (i.e. n_1 and n_2) can be replaced by the patient-years of observation. The chi-square function still has the form given above, but the variance estimate is to be calculated slightly different as explained in [6].

Definition of Geographic Region

Most statistical models will include a term for geographic region. Region will be defined as US, Europe, Asian-Pacific, and Latin-America.

Product: MK-0822

26

Protocol/Amendment No.: 018-04**Ground Rules and Data Handling Conventions***Baseline Definitions or Conventions*

The baseline values for efficacy or safety endpoints used in the analysis will be the measurement closest to the target day (Day 1) for the baseline time window defined below. In case there are 2 measurements on this day, the mean of these 2 measurements will be considered in the analysis.

Time Points, Day Ranges, and Phasing of Study Periods

Since it is generally not possible for all study participants to come in for their clinical visits on the exact day specified in the protocol schedule, relative day ranges will be established for the efficacy and safety variables according to Table 3 to Table 7. The relative day of start of double-blind study medication is Day 1 (based on the prime therapy records), Day -1 is the day before and Day 2 the day after.

Product: MK-0822

27

Protocol/Amendment No.: 018-04

Table 2

Relative Day Ranges for Efficacy Analyses
Morphometric Vertebral Fractures

Time Point (Target Day)	Full-Analysis-Set and Per-Protocol Analyses
Baseline (1)	-90 to 7
Baseline to Month 6 (183)	8 to 228
Month 6 to 12 (365)	229 to 455
Month 12 to 24 (731)	456 to 821

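### Lumbar spine, forearm and total body scans that the protocol accepts as baseline can fall before the Day -90 limit of the BMD analysis window, which leaves those women without a percent change at that site

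*Protocol*

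**What the plan says.** Two parts of the protocol set the age limit of a baseline BMD scan, and they count from different dates.

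- **Acquisition.** Section 3.2.3.6.2 covers lumbar spine scans and, in the 10% subset, total body and distal forearm scans. Scans "obtained within 3 months prior to the screening visit that comply with the study DXA procedures" "may be used, and need not be redone at Randomization". The limit runs back from screening. The same section says: "Within 1 month, eligible patients should return to the clinic for a Randomization visit". The flow chart (Section 1.7) puts that interval at no more than 30 days.
- **Analysis.** Appendix 6.7 (Baseline Definitions or Conventions) says that the baseline value "will be the measurement closest to the target day (Day 1) for the baseline time window defined below". On the time scale it states: "The relative day of start of double-blind study medication is Day 1". Table 3 of the appendix sets the BMD and height baseline window at Day -90 to Day 7. The limit runs back from first dose.

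For the hip, Section 3.2.3.6.1 allows "Hip BMD scans obtained within 90 days prior to the Randomization visit that comply with the study DXA procedures". That rule counts from Randomization and so fits the analysis window closely.

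The BMD endpoints are percent changes from baseline (Section 3.5.3). Lumbar spine and distal forearm belong to the BMD family tested with a Hochberg adjustment (Section 3.5.5.3). Total body BMD is exploratory.

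**The concern.** A site can follow Section 3.2.3.6.2 to the letter and still supply a scan that Table 3 does not recognise as baseline. The longitudinal model handles missing follow-up values, but its response is the percent change. Without a baseline there is no response at any visit, so the woman leaves the analysis for that site. No passage exempts an older scan that was accepted at entry, although Section 3.3.1.2 has all BMD scans evaluated centrally.

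At stake are valid measurements at two formally tested sites. If the team uses the older scans anyway, it departs from its own written rule with nothing pre-specified to support the choice.

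**Working it through.** **1. The plan's own BMD figures.** Section 3.5.5.4 gives SD 4%, two-sided alpha 5% and power 99%, with a detectable difference of 0.3% for 6,000 per group and 1% for 1,200 patients in total.

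MDD = SD × (z0.975 + z0.99) × √(2/n)

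- n = 6,000 per group: 4 × (1.960 + 2.326) × √(2/6,000) = 0.313%
- n = 600 per group: 4 × (1.960 + 2.326) × √(2/600) = 0.990%

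Both agree with the stated figures after rounding.

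**2. Oldest permitted scan.** Inputs:

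- M, the permitted age at screening: 3 months, or 90 to 92 days (Section 3.2.3.6.2).
- g, screening to Randomization: 0 to 30 days (Section 1.7).
- f, Randomization to first dose: 0 to 6 days. This is an assumption. The protocol lets the patient choose her dosing weekday but states no delay.

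The oldest scan lies M + g + f days before Day 1. The excess over the window is M + g + f - 90. If the ages of reused scans are spread evenly over the 3 months (also an assumption), the share of reused scans outside the window is that excess divided by M.

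| M | g | f | Oldest scan | Days outside | Share of permitted range |
|---|---|---|---|---|---|
| 90 | 0 | 0 | Day -90 | 0 | 0% |
| 90 | 14 | 0 | Day -104 | 14 | 15.6% |
| 90 | 21 | 0 | Day -111 | 21 | 23.3% |
| 90 | 30 | 0 | Day -120 | 30 | 33.3% |
| 90 | 30 | 6 | Day -126 | 36 | 40.0% |
| 92 | 30 | 6 | Day -128 | 38 | 41.3% |

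Some gap is built into the design, because no one may be randomized until scans and films have been reviewed centrally (Section 3.2.3.6.2). The shares apply to women whose scan was reused, not to all women.

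**3. Hip, for comparison.** A limit of 90 days before Randomization gives Day -90 with same-day dosing, which is inside the window, and Day -96 with the assumed 6-day delay.

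**4. Effect on precision.** The loss rates below are assumptions, applied to the plan's own sample sizes.

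| Baselines lost | Power for 1% difference, 600 per group before loss | Lumbar spine MDD, 6,000 per group before loss |
|---|---|---|
| 0% | 99.1% | 0.313% |
| 5% | 98.8% | 0.321% |
| 10% | 98.4% | 0.330% |
| 20% | 97.2% | 0.350% |

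The planned enrolment also leaves a margin. Of 16,300 women, (16,300 - 12,000)/16,300 = 26% could lack a spine baseline before the analysis fell to the 12,000 on which the BMD power statement rests.

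**The case against.** The strongest reply is that the mismatch is real but changes no conclusion. Scheduled practice is a new lumbar spine scan at Randomization, so reuse is an exception, and a reused scan must also meet the study's DXA procedures. For forearm and total body, a compliant scan taken before screening in a woman later drawn into the random 10% subset would be largely coincidence. Scan age is fixed before allocation, so any loss is unrelated to treatment. Data-handling rules are in any case to be settled before unblinding. All of this stands and limits the weight of the point. It does not remove the contradiction, and the chance to settle the rule before unblinding is a reason to use it now.

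A reader might infer more than the protocol supports:

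- **That the first primary endpoint is affected**, because spine films may be up to 90 days old at Randomization while Table 2 also starts at Day -90. Sections 3.5.3 and 3.5.4 use all available x-rays and exclude a woman only if she has no scan during the study. The complementary log-log model uses post-baseline periods only and computes no change from baseline.
- **That hip BMD is lost as well.** The hip rule fits the window except under the assumed dosing delay, and then by only a few days.
- **That a definite number of baselines is lost, or that losses cluster in certain sites.** The protocol gives no reuse rate and nothing on its distribution.

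**Conclusion.** The point holds for lumbar spine, distal forearm and total body BMD. A compliant baseline scan can lie at about Day -120 with a 30-day gap and same-day dosing, or at about Day -128 under the longest reading of 3 months and a 6-day dosing delay. Table 3 stops at Day -90 with no fallback. Read literally, the rules discard centrally evaluated baselines for two formally tested secondary endpoints and one exploratory endpoint.

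The number of women is unknown. With evenly spread scan ages, between about one sixth (14-day gap) and one third (30-day gap) of reused scans would fall outside, given same-day dosing. Precision suffers little even at assumed losses of 5% to 20%, and no bias between arms is expected. This is a contradiction that needlessly discards data. It does not make the BMD analyses underpowered, and it does not threaten hip BMD, height or the fracture endpoints.

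**What to change.** Before unblinding, for lumbar spine, distal forearm and total body BMD only, define baseline in Table 3 of Appendix 6.7 as the scan accepted under Section 3.2.3.6.2 and reviewed by the BMD QA center. Alternatively, extend the lower limit for these three sites to about Day -130, which covers the Day -128 extreme. Keep Day 7 as the upper limit and keep the rule that takes the measurement closest to Day 1. Leave Table 2, hip BMD and height as they are.

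Tightening the acquisition rule to match the hip would help little. Section 3.1.1.1 reports 16,716 women already enrolled by September 2011, more than the planned 16,300, so the change belongs on the analysis side.

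The cost is an edit to one table and no new data. The downside is that some baselines will be up to about 4 months old at first dose. The summary of days since start of medication that Appendix 6.7 already plans for each BMD time window would show how often this happens.

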3.2.3.6.4 Month 6 (Visit 4)

The procedures performed at this visit are summarized in Table 3-4 below.

Product: MK-0822

21

Protocol/Amendment No.: 018-04

Table 3-4

List of Procedures – Month 6 (Visit 4)

Perform limited physical exam (including vital signs and weight)
 
Perform lateral spine x-ray
 
Collect blood and urine for laboratory safety assessments[†]
 
Collect blood and urine for lab efficacy assessments and archives[‡]
 
Collect PK sample in first 1500 patients enrolled
 
Meal Questionnaire in first 1500 patients enrolled
 
Dispense study medication (including blinded study therapy, vitamin D₃, and calcium [if needed])
 
Provide diary card
 
Review diary card
 
Perform tablet count for compliance (only for blinded study therapy)
 
Review adverse experiences
 
Review concomitant medication
 
Perform Health Resource Utilization (if fracture has occurred)
 
Spine/hip DXA at 6 months will only be performed in cases where this is required by regulatory agency via documented request, subsequently approved by the SPONSOR. As with all follow-up DXA measurements, results will be blinded unless EBL criteria are met.
 
[†] Laboratory tests for safety assessments need not be drawn in a fasted state.
 
[‡] Efficacy lab tests and archives performed on a 10% subset of patients. These should be fasting specimens, and urine should be second morning void.

3.2.3.6.5 Month 12 (Visit 6)

The procedures performed at this visit are summarized in Table 3-5 below.

Table 3-5

List of Procedures – Month 12 (Visit 6)

Perform limited physical exam (including vital signs, height and weight)
 
Review concomitant medication
 
Collect blood and urine for laboratory safety assessments[†]
 
Collect blood and urine for lab efficacy assessments and archives[‡]
 
Plasma for proteomics archive
 
Perform BMD at the total hip (and subregions) and lumbar spine
 
Perform BMD at the distal forearm and total body[§]
 
Perform Health Resource Utilization (if fracture has occurred)
 
Review adverse experiences
 
Perform lateral spine x-ray[†]
 
Dispense study medication (including blinded study therapy, vitamin D₃, and calcium [if needed])
 
Provide diary card
 
Review diary card
 
Perform tablet count for compliance (only for blinded study therapy)
 
Administer calcium questionnaire
 
[†] Laboratory tests for safety assessments need not be drawn in a fasted state.
 
[‡] Efficacy lab tests are performed on a 10% subset of patients. Archives should be collected in all patients. All samples should be fasting specimens, and urine should be second morning void.
 
[§] BMD at the distal forearm and total body performed on a 10% subset of patients.
 
 The same hip must be scanned as was used at baseline.

Product: MK-0822

22

Protocol/Amendment No.: 018-04**3.2.3.6.6 Months 15, 21, 27, 33, 39, 45 (Visits 7T, 9T, 11T, 13T, 15T, and 17T)**

These are telephone visits, and the procedures conducted are summarized in Table 3-6.

Table 3-6

List of Procedures[†] – Months 15, 21, 27, 33, 39, 45
(Visits 7T, 9T, 11T, 13T, 15T, and 17T)

Review concomitant medications Perform Health Resource Utilization (if fracture has occurred) Review adverse experiences
[†] Since this is an event-driven study that will be stopped once a pre-defined number of fracture events have occurred, not all patients may have all visits detailed in the flow-chart.

3.2.3.6.7 Months 24, 36, 48 (Visits 10, 14, and 18)

The procedures performed at this visit are summarized in Table 3-7 below.

Table 3-7

List of Procedures[†] – Months 24, 36, and 48 (Visits 10, 14, and 18)

Perform BMD at the total hip (and subregions) and lumbar spine [#] Perform BMD at the distal forearm and total body Perform limited physical exam (including vital signs, height and weight) Perform lateral spine x-ray Collect blood and urine for laboratory safety assessments [‡] Collect blood and urine for lab efficacy assessments and archives [§] Administer calcium questionnaire Dispense study medication (including blinded study therapy, vitamin D ₃ , and calcium [if needed]) Provide diary card (if needed) Review diary card Perform tablet count for compliance (only for blinded study therapy) Review adverse experiences Review concomitant medication Perform Health Resource Utilization (if fracture has occurred) In patients undergoing transilial bone biopsy at Month 24 and/or Month 36: 
 • Obtain informed consent for transilial bone biopsy approximately 1 month before biopsy • Dispense bone labeling agent approximately 1 month before biopsy • Perform transilial bone biopsy
[†] Since this is an event-driven study that will be stopped once a pre-defined number of fracture events have occurred, not all patients may have all visits detailed in the flow-chart. [‡] Laboratory tests for safety assessments need not be drawn in a fasted state. [§] Efficacy lab tests are performed on a 10% subset of patients. Archives collected in 10% subset except at the end of the study when archives will be collected in everyone. All should be fasting specimens, and urine should be second morning void. BMD at the distal forearm and total body performed on a 10% subset of patients. [#] The same hip must be scanned as was used at baseline.

Product: MK-0822

23

Protocol/Amendment No.: 018-04**3.2.3.6.8 Month 24 (Visit 10) and/or Month 36 (Visit 14): Transilial Bone Biopsy**

At participating clinical centers, a transilial bone biopsy will be performed at Month 24 and/or Month 36. Biopsies will be optional for patients and will be done based on a separate informed consent, administered approximately 1 month before the biopsy, prior to any biopsy-related procedures being performed. Patients undergoing this procedure at Month 24 will be provided with an acceptable bone labeling agent at **Month 23** (e.g. demeclocycline or other tetracycline), which will be sourced locally. Patients undergoing this procedure at Month 36 will be provided with an acceptable bone labeling agent at **Month 35**. Patients with bleeding disorders will not be able to undergo a transilial biopsy. Further details of the biopsy procedure, including additional patient requirements for inclusion, will be provided in a separate SOP. It is anticipated that approximately 200 biopsies will be obtained study-wide at Month 24 and approximately 200 biopsies will be obtained at Month 36.

